11.3. Subject Screening

Pre-screening of potential subjects may be over the telephone or in person (e.g. during a routine clinical care), to determine their initial eligibility and interest in the study.

Final screening of potential subjects needs to be in person on the day of the MASS2 visit, to verify that the subject is not in atrial fibrillation, as per exclusion criterion.

11.4. Prior and Concomitant Medications

There is no restriction about prior or concomitant medication/treatment. Subjects who had already received MATS software in MASS can receive MATS software download again in MASS2.

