6.1. Objective

The primary objective of MASS2 is to collect and characterize the waveform and components of the accelerometer signal from the Micra implantable device during different postures and activities, and to use echocardiography recordings to understand the elements contributing to the accelerometer signal.

This objective is descriptive and therefore no endpoints will be developed.

There are no secondary objectives (therefore no secondary endpoints) for MASS2.

7. Study Design

The MASS2 is a prospective non-randomized, multi-center clinical research study, designed to extend and advance data collection of its predecessor, the MASS study.

This document is electronically controlled. Printed copies are considered uncontrolled.

Confidential

The study will be conducted in Europe and may include countries such as Austria, France and Spain. The study is expected to be conducted at approximately four centers. Between 40 and 50 subjects are expected to be enrolled in order to collect a representative sample of approximately 40 readable datasets. Since the study will be exploratory in nature, no statistical hypotheses were formulated to calculate the sample size and the number of expected subjects was based on the experience from the previous MASS study.

Centers that enroll faster than others will be allowed to do so in order to maintain an adequate enrollment rate, and therefore there is not a minimum or maximum requirement for the number of subjects enrolled at each center.

The Micra Accelerometer and Temperature Sensor (MATS) Research System was developed in support of the MASS study to allow collection of data from the Micra sensors. MASS2 will use the unchanged MATS Research System for the same purposes of MASS.

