7.2. Rationale

The previous MASS study was developed to collect data from the sensors of the Micra device, using the MATS Research System. All pre-clinical testing on the MATS Research System were executed in support of the MASS study and the results showed that all tests have successfully passed. MASS study enrolled 40 subjects. Neither adverse events nor device deficiencies related to MASS system/procedures were reported during the MASS study. Usable recordings were obtained from 32 of the subjects. The continuous accelerometer signal was used to develop a preliminary algorithm to detect atrial contractions using the accelerometer in the right ventricle. The 20 recordings in sinus rhythm were processed and the accuracy of the atrial detection algorithm was assessed. A larger sinus rhythm data set is desired for a wider representation of subjects and for further algorithm development. Therefore, MASS2 is being proposed to record additional subjects to extend the data set, using the unchanged MATS Research System. Furthermore, MASS2 will also collect echocardiography recordings to characterize the source of the accelerometer signal from the intracardiac accelerometer.

With the FDA and CE approval of the Micra device and the resulting launch of closure activities of the Micra Transcatheter Pacing Study (IDE Number: G130245), MASS2 is designed as an independent/stand-alone study.

This document is electronically controlled. Printed copies are considered uncontrolled.

Confidential

8. Product Description

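### Does letting MASS participants re-enter MASS2 undercut the aim of recording additional subjects?

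*Combined protocol and SAP*

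**What the plan says.** Section 11.4 permits re-entry without a cap: "Subjects who had already received MATS software in MASS can receive MATS software download again in MASS2". Neither exclusion criterion in Section 9.4 concerns prior MASS participation.

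Section 7.2 gives the reason for a second study. It reports that "MASS study enrolled 40 subjects", with usable recordings from 32. On their use it says "The continuous accelerometer signal was used to develop a preliminary algorithm to detect atrial contractions using the accelerometer in the right ventricle" and "The 20 recordings in sinus rhythm were processed and the accuracy of the atrial detection algorithm was assessed". It continues: "A larger sinus rhythm data set is desired for a wider representation of subjects and for further algorithm development", and "Therefore, MASS2 is being proposed to record additional subjects to extend the data set, using the unchanged MATS Research System". The same paragraph adds a second reason: echocardiography, to find out what produces the accelerometer signal.

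Section 7 describes MASS2 as "designed to extend and advance data collection of its predecessor, the MASS study" and sets its size: "Between 40 and 50 subjects are expected to be enrolled in order to collect a representative sample of approximately 40 readable datasets". Section 6.1 calls the objective descriptive and sets no endpoints. Section 15 plans no hypothesis test and says the number of subjects in each analysis will be reported. No section says whether prior MASS participation will be recorded, or how a person present in both studies would be handled.

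**The concern.** The stated need is for more people in sinus rhythm, but the target is counted in readable datasets. On a plain reading, a returning MASS participant who passes the atrial fibrillation exclusion and gives a readable dataset fills one of the 40 places. If that person is already among the 20 MASS sinus-rhythm recordings, the sinus-rhythm set gains a recording but not a person.

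Three things would be at stake. The number of new people could fall below the readable count without a reader seeing it. If the two studies were combined and each recording counted as a separate person, the number of people would be overstated and the uncertainty understated. If the atrial detection algorithm from MASS were evaluated on MASS2 recordings, part of that evaluation would use people who had already contributed to building or assessing it.

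**Working it through.** **The plan's own figure.** MASS gave 32 usable recordings from 40 subjects: 32/40 = 0.80. To obtain 40 readable datasets at that rate takes 40/0.80 = 50 enrolments, which matches the upper end of the 40 to 50 range. Returning subjects do not enter this calculation.

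**Who could return.** Section 7.2 divides the 40 MASS subjects into 20 with a processed sinus-rhythm recording, 32 − 20 = 12 with a usable recording outside that group, and 40 − 32 = 8 with no usable recording. Only the first 20 can duplicate a person in the sinus-rhythm set. Any of the other 12 + 8 = 20 who is in sinus rhythm on the day and gives a readable recording adds a person to it.

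**Size if the two sets were combined.** Let k be the number of returners from the first 20. The documents do not give k, so a range from 0 to the ceiling of 20 is used. Assume each returner gives one readable dataset and all 40 MASS2 datasets are in sinus rhythm. The combined set then has 20 + 40 = 60 recordings from 60 − k people. For a simple mean, with correlation ρ between two recordings of one person, the variance relative to independence is 1 + 2kρ/60, and the standard error ratio is its square root. The documents give no ρ; 0.5 and 0.8 are assumed.

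| k | New people, 40 − k | Distinct people, 60 − k | Overcount, 60/(60 − k) − 1 | Share of MASS2 from returners, k/40 | SE ratio, ρ = 0.5 | SE ratio, ρ = 0.8 |
|---|---|---|---|---|---|---|
| 0 | 40 | 60 | 0% | 0% | 1.00 | 1.00 |
| 5 | 35 | 55 | 9% | 12.5% | 1.04 | 1.06 |
| 10 | 30 | 50 | 20% | 25% | 1.08 | 1.13 |
| 20 | 20 | 40 | 50% | 50% | 1.15 | 1.24 |

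For example, k = 10 with ρ = 0.5 gives 1 + 2 × 10 × 0.5/60 = 1.167, with square root 1.08. A nominal 95% interval that ignored the pairing would cover about 93% (ρ = 0.5) or 92% (ρ = 0.8) at k = 10, and about 91% or 89% at k = 20.

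**Whether the plan contains such an analysis.** It does not. Section 15 names no pooled MASS and MASS2 estimate, standard error, confidence interval or accuracy measure. Section 11.6 limits comparisons to describing the study population. Within MASS2 a returner contributes one dataset, so no within-person pairing arises and the variance factor is 1.

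**What a returner adds.** Section 7 identifies echocardiography as the procedure that is new relative to MASS, and Section 11 keeps the accelerometer recording running during it. Section 5.1 says MASS left the source of the motion unclear. For the echo half of the primary objective, a returner therefore gives as much new information as a first-time participant.

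**Whether returners can be identified.** Section 8.1.3 requires an access code, unique to each device serial number and issued by the study team, before the software can communicate with a device. Section 17.5 requires sites to keep screening and identification logs. Assuming the MASS serial numbers were kept, matching is a clerical task.

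**The case for a change.** The strongest case for a change is that the sponsor foresaw re-entry, since Section 11.4 provides for it, and that Section 7.2 speaks of extending the data set, which makes eventual combination a natural reading. The per-analysis subject counts in Section 15 are there to show the effect of missing data and would not reveal a person present in both studies. That returners could be matched by serial number does not mean anyone has undertaken to do it. One baseline field and a sentence or two in Section 15 would settle the matter at almost no cost.

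Much of this is true. The documents do not say that prior participation will be flagged, and a returner from the 20 sinus-rhythm recordings does not broaden that set. Three things limit its weight. First, Section 11.4 allows a second software download and says nothing about the target; that such datasets count toward the 40 is inferred from silence. Second, the e-CRF is not among the documents, so it cannot be shown that the field is absent. Third, rules for distinct people and paired recordings belong in the plan of whatever combined analysis is later written, because MASS2 has no analysis to which they would apply. Section 7.2 also speaks of further algorithm development and does not promise an independent validation.

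**Conclusion.** No change is needed. The two sections pull in different directions on one of the study's two reasons, but admitting MASS participants is a fair trade-off: they may add little breadth to the sinus-rhythm set, while they add fully to the echo data. The planned MASS2 descriptive results are sound as written for any number of returners.

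The possible distortion runs from nothing at k = 0 to a 50% overcount of people and a standard error 15% to 24% larger than reported at k = 20. It would arise only in a combined analysis that the documents do not specify, and only if that analysis ignored the pairing. Those figures rest on an unknown k, an assumed correlation of 0.5 to 0.8, and all 40 MASS2 datasets being in sinus rhythm. Anyone combining the sets would ordinarily match devices first and report people as well as recordings. Stating in the MASS2 report how many readable datasets came from earlier MASS participants would be ordinary good practice and does not depend on amending the plan.

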11.5. Subject Consent

Informed Consent (IC) is defined as a legally effective documented confirmation of a subject's voluntary agreement to participate in a particular clinical study after information has been given to the subject on all aspects of the clinical study that are relevant to the subject's decision to participate. This process includes obtaining an ICF and other privacy language as required by law that has been approved by the study center's EC and signed and dated by the subject. A subject may only consent after information has been given to the subject on all aspects of the clinical investigation that are relevant to the subject's decision to participate.

Prior to enrolling subjects, each center's EC will be required to approve the ICF and other privacy language as required by law. The document(s) must be controlled (i.e. versioned and/or dated) to ensure it is clear which version(s) were approved by the EC. Any adaptation of the sample ICF must be reviewed and approved by Medtronic and the EC reviewing the application prior to enrolling subjects.

The investigator must notify the subject of any significant new findings about the study that become available during the course of the study which are pertinent to the safety and well-being of the subject,

This document is electronically controlled. Printed copies are considered uncontrolled.

Confidential

as this could impact a subject's willingness to participate in the study. If relevant, approval may be requested from subjects to confirm their continued participation.

ICF templates will be provided under a separate cover.

Prior to initiation of any study-specific procedures, IC must be obtained from the subject. Likewise, privacy or health information protection regulation may require subjects to sign additional forms to authorize centers to submit subject information to the study sponsor. The IC process must be conducted by the principal investigator or an authorized designee, and the ICF and other privacy language as required by law must be given to the subject in a language he/she is able to read and understand. The process of IC must be conducted without using coercion or undue improper influence on or inducement of the subject to participate by the investigator or other center personnel. The IC process shall not waive or appear to waive subject's legal right. The language used shall be as non-technical as possible and must be understandable to the subject and the impartial witness, where applicable.

The subject must have ample time and opportunity to read and understand the ICF, to inquire about details of the study, and to decide whether or not to participate in the clinical study. All questions about the study should be answered to the satisfaction of the subject.

When the subject decides to participate in the clinical study, the IC must be signed and personally dated by the subject and investigator or authorized designee, as required by the ICF.

If the IC is obtained the same day the subject begins participating in study-related procedures, it must be documented in the subject's case history that consent was obtained prior to participation in any study-related procedures. It is best practice for the IC process to be documented in the subject's case history, regardless of circumstance.

In the event the subject cannot read and/or write and if allowed by local law the IC process shall be obtained through a supervised oral process. An independent witness (if applicable as per local regulation) must be present during this process. The IC and any other information must be read aloud to the prospective subject or his/her legally authorized representative. The witness signs and personally dates the IC attesting that the information was accurately explained and that IC was freely given.

The IC should document the method used for communication with the prospective subject and the specific means by which the prospective subject communicated agreement to participate in the study.

The original of the signed ICF must be filed in the hospital/clinical chart and/or with the subject's study documents.

A copy of the ICF and other privacy language as required by law, signed and dated as required by law, must be provided to the subject.

The ICF and other privacy language as required by law and must be available for monitoring and auditing. Any Medtronic Field personnel who support the study procedure must be able to review the subject's signed and dated ICF and verify its completeness prior to proceeding with the study procedure. In the event the Medtronic Field personnel identify IC as being incomplete, the study procedure will not be allowed to occur until the consent of the subject can be adequately and appropriately obtained.

11.6. Randomization and Treatment Assignment

The study is not randomized. There is no comparison to a control group. There will not be statistical comparisons except to describe the study population.

This document is electronically controlled. Printed copies are considered uncontrolled.

Confidential

11.7. Treatment Compliance

Subject compliance to the Holter and echo examinations will be monitored with a periodical review of received data.

11.8. Recording Data

Subject data and product accountability data will be collected on the e-CRFs and will be reported to Medtronic via the RDC System, Oracle Clinical.

Device interrogation data will be saved on supported media and will be delivered either electronically via a secure web-based application (Clinical Transfer or BOX) or via mail. Device data are recommended and not mandatory. Missing device interrogation data should not be considered as deviation.

ECG and accelerometer data will be saved on the Holter flashcard and will be delivered either electronically via a secure web-based application (Clinical Transfer or BOX) or via mail.

Echo data will be saved on supported media and will be delivered either electronically via a secure web-based application (Clinical Transfer or BOX) or via mail.

11.9. Deviation Handling

A study deviation is defined as an event within a study that did not occur according to the CIP or the CTA.

Prior approval by Medtronic is expected in situations where the investigator anticipates, contemplates, or makes a conscious decision to deviate. Prior approval is not required when a deviation is necessary to protect the safety, rights or well-being of a subject in an emergency or in unforeseen situations beyond the investigator's control (e.g. inadvertent loss of data due to computer malfunction, inability to perform required procedures due to subject inability).

For medically justifiable conditions which preempt a subject's ability to complete a study-required procedure, it may be permitted to report only one deviation which will apply to all visits going forward. This may also apply for other unforeseen situations (e.g. the subject permanently refuses to complete a study required procedure and the data will not contribute to the primary end point analysis). However, prior approval from Medtronic is required for such situations.

All study deviations must be reported on the e-CRF regardless of whether medically justifiable, pre-approved by Medtronic, an inadvertent occurrence, or taken to protect the subject in an emergency. Multiple deviations of the same type at the same visit may be reported on one e-CRF.

In the event the deviation involves a failure to obtain a subject's consent, or is made to protect the life or physical well-being of a subject in an emergency, the deviation must be reported to the EC as well as Medtronic. Reporting of all other study deviations should comply with EC policies and/or local laws and must be reported to Medtronic as soon as possible upon the center becoming aware of the deviation. Reporting of deviations must comply with EC policies, local laws, and/or regulatory agency requirements.

The investigator is not allowed to deviate from the CIP, except under emergency circumstances to protect the rights, safety and well-being of human subjects.

Medtronic is responsible for analyzing deviations, assessing their significance, and identifying any additional corrective and/or preventive actions (e.g. amend the CIP, conduct additional training, and terminate the investigation). Repetitive or serious investigator compliance issues may result in initiation of a corrective action plan with the investigator and site, and in some cases, necessitate suspending

enrollment until the problem is resolved or ultimately terminating the investigator's participation in the study.

Examples of MASS2 deviations include but are not limited to:

- 1 Failure to obtain subject IC
- 2 Inclusion/exclusion criteria not met
- 3 Missing ECG /accelerometer/echo data

11.10. Subject Withdrawal or Discontinuation

If a subject is withdrawn from the clinical study, the reason for withdrawal will be recorded in the e-CRF and in the subject's hospital record. Possible reasons for withdrawal from the study are:

- Subject withdrew consent;
- Investigator withdrew subject from the study for technical reasons (e.g. unsuccessful software download or Holter telemetry);
- Investigator withdrew subject from the study for medical reasons (e.g. inability to complete posture and exercise test);
- Investigator withdrew subject from the study due to inclusion/exclusion criteria not met.

If withdrawal is because of a safety concern, the subject shall be asked to be followed by the physician for collecting safety data outside the clinical study.

Subjects who are withdrawn before they complete the study can be replaced with new enrollments in order to collect a representative sample of approximately 40 readable datasets.

Since the study procedures will occur all on the same day, lost-to-follow up is not expected to occur.

12. Risks and Benefits

12.1. Potential Risks

Medtronic follows rigorous Quality Assurance and Control procedures throughout the development and clinical study of a product. The formal Hazard/Risk analysis of MATS Research System was done for the MASS study according to ISO 14971 (Medical Device Risk Management) and was used to ensure that the level of risk is acceptable prior to starting the MASS study.

MASS2 will use the same MATS Research System used in MASS (Table 1) and for the same purpose to allow collection of data from the Micra sensors. MASS2 procedures are similar to MASS. The main change in procedures is the addition of the echo examination performed with the echo machine available at the hospital. The echo procedure poses negligible / no risk to the subjects. Therefore, the formal Hazard/Risk analysis of MATS Research System which was done for MASS will not be impacted by MASS2, due to no new or increased risk as an outcome of the study. The comprehensive Hazard Analysis is documented in the MATS Research System Risk Management Report (DSN017848 Version 2.0 Initial Release).

During the course of the MASS2 study, risks will be continuously monitored, assessed and documented by the investigators. The risks are reduced as much as possible, with residual risk being documented within the Risk Management Report and disclosed in the ICF provided to subjects. A list of potential risks, mitigations and risk controls associated with the MASS2 product and procedure is summarized in Table 3 and Table 4.

This document is electronically controlled. Printed copies are considered uncontrolled.

Confidential

Any potential risks associated with this study are further minimized by selecting qualified investigators, training study personnel on the Clinical Investigation Plan and User Manual.

Table 3 - Potential product risks and risk minimization

Potential product risk	Minimization

Improper MATS software download and manual removal:
 
Download and manual removal of the MATS software from the Micra device, if done improperly may impact implanted device functionality.
	
 Access codes, software version, and software limitation requirements (no other software present in the device RAM) are in place for MATS software download Programmer user is informed of presence of MATS investigational software on the Micra device on user interface If the download of the MATS software does not execute correctly, this will be detected by the Micra device and the software will not be activated The MATS software can be manually removed from the Micra device. The MATS software has an internal timer that automatically deactivates the software 48 hours after download

Interactions of the MATS software with existing Micra device features:
 
MATS software runs from the device RAM and sends the accelerometer and temperature sensor data via telemetry to the ER220 Holter, potentially causing an unintended interaction.
	
 Potential Micra device interactions with the MATS software running with existing Micra device were analyzed. Interactions were limited to the use of telemetry for sensor data uplink and rate response, which were identified to be low risk as no direct therapeutic functionality would be affected. Verification activities will be performed to ensure no related negative interactions

Missing/ misleading information causing insufficient/ inappropriate medical intervention:
 
Errors, omissions, or ambiguities in diagnostic data collected/ presented to the user, or corruption of software that influences the user's ability to make an informed medical decision.
	
 Misleading information is prevented because MATS temperature sensor data is not viewable by study center personnel and any data not used for diagnosis purposes Data integrity is controlled via ECC memory checks in the Micra device Information on MATS supplemental markers on real-time EGM will be provided in training and User Manual User Manual will instruct investigator to program optimum accelerometer vector in subject' Micra devices prior to leaving the study

Device longevity:
 
The sensor functionality and telemetry uplink mode will cause a slight current drain on the Micra device.
	
 Risk control measures have been implemented to prevent longevity impacts greater than three months by limiting the duration of uplink of sensor data using telemetry to a maximum of 24 hours The MATS feature set has an internal timer that automatically deactivates the software 48 hours after download The MATS software download into the Micra Device will be prevented if the device is at pre-RRT (Recommended Replacement Time)

This document is electronically controlled. Printed copies are considered uncontrolled.

Confidential

Table 4- Potential procedure risks and risk minimization

Potential procedure risk	Minimization
Excessive exertion from MASS2 Posture and Exercise Test may worsen subject's health conditions.	
 Subjects will not be enrolled in the MASS2 if unwilling or not able to perform study requirements Subject is allowed to have recovery time during the test as needed.
Inappropriate pacing: The procedure includes steps to set temporary pacing rate approximately 10 bpm above the subject's intrinsic rhythm to collect accelerometer data during pacing	
 Subjects are under the supervision of an experienced Clinician during the protocol steps Detailed instructions in the MASS2 worksheets instructing overdrive pacing at a rate ~ 10bpm higher than the intrinsic heart rate Temporary pacing allows immediate cancellation / cessation of pacing if needed due to subject symptom There are no potential interactions of the MATS software with the temporary parameters of the Micra device

